### 6.8.3 Permitted Therapy

Subjects are permitted the use of topical, ocular, intra-articular, intranasal, and inhalational corticosteroids (with minimal systemic absorption). Adrenal replacement steroid doses  $> 10$  mg daily prednisone are permitted. A brief (less than 3 weeks) course of corticosteroids for prophylaxis (eg, contrast dye allergy) or for treatment of non-autoimmune conditions (eg, delayed-type hypersensitivity reaction caused by a contact allergen) is permitted. Regular

---

CONFIDENTIAL

*This document is confidential. Do not disclose or use except as indicated.*

IRB APPROVED

concomitant use of bisphosphonates and RANK-L inhibitors for prevention or reduction of skeletal-related events in subjects with bone metastases is allowed if initiated prior to first dose of study therapy. Prior palliative radiotherapy must have been completed at least 4 weeks prior to treatment.

For patients with differentiated or medullary disease, prior palliative radiotherapy must have been completed at least 8 weeks prior to randomization for cases of radiotherapy to the head and neck, and completed within 4 weeks prior to randomization for radiotherapy to other sites. On study palliative radiotherapy is only allowed for treatment of painful bone lesions. Palliative surgical resection of tumor sites is not permitted. Subjects requiring palliative radiotherapy should be evaluated for objective evidence of disease progression prior to the initiation of such therapy, particularly if the most recent tumor assessment was more than 4 weeks prior to the start of local therapy. If progression per RECIST 1.1 is identified on any tumor assessments prior to the initiation of palliative local therapy, then subjects must either discontinue study drug treatment or they must meet criteria to continue treatment beyond progression in order to resume immunotherapy after palliative local therapy.

Due to the aggressive nature of their disease, anaplastic thyroid cancer patients may receive palliative radiation to non-bone sites and/or resection at the investigator's discretion. For these patients, the washout period for radiation will be at the investigator's discretion.

The potential for overlapping toxicities with radiotherapy and nivolumab/ipilimumab currently is not known; however, anecdotal data suggests that it is tolerable. As concurrent radiotherapy and nivolumab/ipilimumab have not been formally evaluated, in cases where palliative radiotherapy is required for a tumor lesion, then nivolumab/ipilimumab should be withheld for at least 1 week before, during, and 1 week after radiation. Subjects should be closely monitored for any potential toxicity during and after receiving radiotherapy, and AEs should resolve to Grade  $\leq 1$  prior to resuming nivolumab or nivolumab plus ipilimumab.

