#### **3.1 Inclusion Criteria**

1. Metastatic, RAI-refractory, differentiated thyroid cancer (including papillary and follicular thyroid cancer and their sub-types such as Hurthle cell thyroid cancer as well as poorly differentiated thyroid cancer), medullary thyroid cancer, or anaplastic thyroid cancer. RAI-refractoriness is not required for medullary or anaplastic thyroid cancer patients. Patients who are not candidates for RAI therapy, as determined by the investigator, are also eligible.

RAI-refractoriness is defined as absence of uptake of RAI on either a low-dose diagnostic test or a post-treatment RAI scan in measurable lesions or radiographic progression of disease within 12 months of the last course of RAI treatment despite the recorded uptake of RAI with that previous therapy or having a cumulative lifetime administered dose of greater than 600mCi.

2. Patients must have experienced disease progression within 13 months prior to study registration, have experienced intolerable side effects on a tyrosine kinase inhibitor (TKI), or be not suitable candidates for TKI. No progression is required for patients with anaplastic thyroid cancer.
3. Age 18 years or older
4. Any number of prior treatments allowed for patients under 65y, over 65y, if suitable candidate for TKI therapy, must have at least one prior line of TKI treatment (excluding medullary and anaplastic patients)

5. ECOG performance status  $\leq 2$  (Karnofsky  $\geq 60\%$ , see Appendix A).

Measurable disease by per RECIST 1.1 criteria (see section 11). Radiographic tumor assessment performed within 28 days of registration

6. Participants must have normal organ and marrow function as defined below:

Screening laboratory values must meet the following criteria and should be obtained within 21 days prior to randomization/registration

- WBC  $\geq 2000/\mu\text{L}$
- Neutrophils  $\geq 1200/\mu\text{L}$
- Platelets  $\geq 100 \times 10^3/\mu\text{L}$
- Hemoglobin  $> 8.0 \text{ g/dL}$
- Serum creatinine  $\leq 1.5 \times \text{ULN}$  or creatinine clearance (CrCl)  $\geq 40 \text{ mL/min}$  (if using the Cockcroft-Gault formula below):

$$\text{Female CrCl} = \frac{(140 - \text{age in years}) \times \text{weight in kg} \times 0.85}{72 \times \text{serum creatinine in mg/dL}}$$

$$\text{Male CrCl} = \frac{(140 - \text{age in years}) \times \text{weight in kg} \times 1.00}{72 \times \text{serum creatinine in mg/dL}}$$

- AST/ALT  $\leq 3 \times \text{ULN}$

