### **3.2 Exclusion Criteria**

1. Patients should be excluded if they have an active, known or suspected autoimmune disease. Subjects are permitted to enroll if they have vitiligo, type I diabetes mellitus, residual hypothyroidism due to autoimmune condition only requiring hormone replacement, psoriasis not requiring systemic treatment, or conditions not expected to recur in the absence of an external trigger
2. Diagnosed or treated for another malignancy within 2 years before administration of the first dose of study drug, or previously diagnosed with another malignancy and have any evidence of residual disease. Patients with nonmelanoma skin cancer or carcinoma in situ of any type are not excluded if they have undergone complete resection.
3. Patients should be excluded if they have a condition requiring systemic treatment with either corticosteroids ( $> 10$  mg daily prednisone equivalents) or other immunosuppressive medications within 14 days of study drug administration. Inhaled or topical steroids and adrenal replacement doses  $> 10$  mg daily prednisone equivalents are permitted in the absence of active autoimmune disease.
4. As there is potential for hepatic toxicity with nivolumab or nivolumab/ipilimumab combinations, drugs with a predisposition to hepatotoxicity should be used with caution in patients treated with nivolumab-containing regimen.
5. Patients who have had chemotherapy/radiotherapy and/or targeted agents within 2 weeks (6 weeks for nitrosoureas or mitomycin C) prior to entering the study or those who have not recovered from adverse events due to agents administered more than 4 weeks earlier. For patients with anaplastic thyroid cancer or otherwise particularly aggressive disease (as determined by the investigator), the washout period for chemotherapy/radiotherapy and/or targeted agents will be at the investigator's discretion.
6. Patients who are receiving any other investigational agents.
7. Patients with active brain metastases should be excluded from this clinical trial because of their poor prognosis and because they often develop progressive neurologic dysfunction that would confound the evaluation of neurologic and other adverse events.
8. Uncontrolled intercurrent illness including, but not limited to, ongoing or active infection, symptomatic congestive heart failure, unstable angina pectoris, cardiac arrhythmia, or psychiatric illness/social situations that would limit compliance with study requirements.

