## **4. REGISTRATION AND RANDOMIZATION PROCEDURES**

### **4.1 General Guidelines for DF/HCC Institutions**

Institutions will register eligible participants in the Clinical Trials Management System (CTMS) OnCore. Registrations must occur prior to the initiation of protocol therapy. Any participant not registered to the protocol before protocol therapy begins will be considered ineligible and registration will be denied.

An investigator will confirm eligibility criteria and a member of the study team will complete the protocol-specific eligibility checklist.

For DTC and MTC patients, the eligibility checklist and all pages of the consent form will be faxed to the ODQ [REDACTED]. The ODQ Registrar will (a) review the eligibility checklist, (b) register the participant on the protocol, and (c) randomize the participant.

For ATC patients, who will not undergo randomization, the study team is responsible for registering patients in OnCore.

An email confirmation of the registration and/or randomization will be sent to the Overall PI, study coordinator(s) from the Lead Site, treating investigator and registering person immediately following the registration and/or randomization.

Following registration, participants may begin protocol therapy. Issues that would cause treatment delays should be discussed with the Overall Principal Investigator (PI). If a participant does not receive protocol therapy following registration, the participant's registration on the study must be canceled. Registration cancellations must be made in OnCore as soon as possible.

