#### 11.1.3 Methods for Evaluation of Disease

All measurements should be taken and recorded in metric notation using a ruler, calipers, or a digital measurement tool. All baseline evaluations should be performed as closely as possible to the beginning of treatment and never more than 4 weeks before the beginning of the treatment.

The same method of assessment and the same technique should be used to characterize each identified and reported lesion at baseline and during follow-up. Imaging-based evaluation is preferred to evaluation by clinical examination unless the lesion(s) being followed cannot be imaged but are assessable by clinical exam.

**Clinical lesions.** Clinical lesions will only be considered measurable when they are superficial (e.g., skin nodules and palpable lymph nodes) and  $\geq 10$  mm in diameter as assessed using calipers (e.g., skin nodules). In the case of skin lesions, documentation by color photography, including a ruler to estimate the size of the lesion, is recommended.

**Chest x-ray.** Lesions on chest x-ray are acceptable as measurable lesions when they are clearly defined and surrounded by aerated lung; however, CT is preferable.

---

CONFIDENTIAL

*This document is confidential. Do not disclose or use except as authorized.*

IRB APPROVED

Conventional CT and MRI. This guideline has defined measurability of lesions on CT scan based on the assumption that CT thickness is 5mm or less. If CT scans have slice thickness greater than 5 mm, the minimum size of a measurable lesion should be twice the slice thickness. MRI is also acceptable in certain situations (e.g. for body scans).

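### Section 6.8.3 sets a maximum instead of a minimum interval between palliative radiotherapy outside the head and neck and randomization for DTC/MTC, so any washout of 29 days or more fails as written

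*Combined protocol and SAP*

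**What the plan says.** Section 6.8.3 gives a general rule for prior palliative radiotherapy: "Prior palliative radiotherapy must have been completed at least 4 weeks prior to treatment". The next paragraph gives a rule for differentiated (DTC) and medullary (MTC) disease, counted from randomization and split by site. Head-and-neck radiotherapy must have been completed "at least 8 weeks prior to randomization for cases of radiotherapy to the head and neck". Radiotherapy elsewhere must have been "completed within 4 weeks prior to randomization for radiotherapy to other sites". For anaplastic disease the washout is left to the investigator.

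Four other places bear on the reading:

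- Section 3.2, exclusion 5, bars patients who had "chemotherapy/radiotherapy and/or targeted agents within 2 weeks (6 weeks for nitrosoureas or mitomycin C) prior to entering the study". The investigator may vary this for anaplastic or otherwise particularly aggressive disease.
- Section 4.1 says "Following registration, participants may begin protocol therapy" and sets no limit on the time from registration to first dose.
- Section 3.1 asks for "Radiographic tumor assessment performed within 28 days of registration", and section 11.1.3 says baseline evaluations are "never more than 4 weeks before the beginning of the treatment".
- For radiotherapy given on study, section 6.8.3 says "nivolumab/ipilimumab should be withheld for at least 1 week before, during, and 1 week after radiation".

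**The concern.** A washout rule sets the least time that must pass after a treatment. The clause for other sites sets the most time that may pass. It admits a patient whose bone metastasis was irradiated 28 days before randomization and rejects one irradiated 90 days before. The protocol gives no reason for requiring recent radiotherapy, and every neighbouring radiotherapy rule is a minimum. A drafting slip that reversed the rule is by far the likeliest explanation.

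What is at stake is who may enter. Followed to the letter, the clause turns away DTC and MTC patients with an ample washout. It also leaves room for a second reading, in which the specific clause displaces the general sentence and the required washout becomes shorter than 4 weeks.

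**Working it through.** The plan gives no figure on this point, so the check is a day count.

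**Definitions**

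- d = days from end of radiotherapy to randomization.
- g = days from randomization to first dose. The plan does not state it, so it is assumed to lie between 0 and 28. The upper end follows from 3.1 and 11.1.3: the baseline scan precedes registration and may be no more than 28 days old at first dose, unless the patient is rescanned.

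**Conditions for DTC/MTC, sites other than head and neck.** *Within* is read inclusively in both places where it occurs.

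1. DTC/MTC clause of 6.8.3: d ≤ 28.
2. General sentence of 6.8.3: d + g ≥ 28.
3. Exclusion 5, counting study entry as randomization and not using the investigator's discretion: d > 14, that is d ≥ 15.

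**Step 1, the clause alone.** d = 14, 21, 27 and 28 satisfy condition 1. d = 29, 35, 56 and 90 do not. Since g does not enter condition 1, every d ≥ 29 fails whatever the gap.

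**Step 2, all three conditions.** The smallest passing d is max(15, 28 − g) and the largest is 28.

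| g (days) | passing d | number of dates |
|---|---|---|
| 0 | 28 | 1 |
| 3 | 25-28 | 4 |
| 7 | 21-28 | 8 |
| 14, 21 or 28 | 15-28 | 14 |

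Condition 2 guarantees at least 28 days from radiotherapy to first dose for everyone who passes. On this reading the fault is over-exclusion, not too short a washout.

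**Step 3, the DTC/MTC clause replaces the general sentence.** Condition 2 drops out and d = 15-28 passes at every gap. The earliest first dose is 15 + g days after radiotherapy: 15 at g = 0, 18 at g = 3, 22 at g = 7.

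**Step 4, corrected clause (d ≥ 28).** Then d + g ≥ 28 for every g ≥ 0, and d ≥ 15 holds as well. The three rules no longer conflict, and 29, 35, 56 and 90 days all pass.

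**Step 5, cost of the correction against Step 2.** The added wait is 28 − max(15, 28 − g) = min(g, 13): 0, 3 and 7 days at gaps of 0, 3 and 7, and 13 days at gaps of 14 or more.

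**The case against.** The strongest reply is that nobody would apply the clause literally. It would bar a patient irradiated years ago, and the text on either side of it makes a minimum the obvious intent. Sites may already apply it that way. Moreover, 6.8.3 sits under concomitant treatments. Section 5.2 points to Section 3 for eligibility, and registration under 4.1 runs on an eligibility checklist that is not in the documents. The Section 3 rule is exclusion 5, which a patient at 29 days or more passes.

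Much of this stands. The intent is clear, and nothing shows that the checklist takes its radiotherapy rule from 6.8.3. It does not remove the point. The clause is worded as a requirement tied to randomization, and Section 3 does not correct it, because exclusion 5 is a separate 2-week minimum. A protocol should not depend on sites disregarding its text.

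A reader might infer three stronger things that the documents do not support:

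- *That sites are applying the rule in opposite directions.* The wording allows it, but nothing shows that it happens.
- *That patients are exposed to harm from a short washout.* The general sentence, if applied, keeps first dose at least 28 days away, and 6.8.3 itself accepts on-study palliative radiotherapy with a 1-week hold on each side.
- *That the primary analysis is affected because its population is restricted to eligible DTC patients.* The plan does not say how many patients have had such radiotherapy, and the washout is not an input to the two-stage design figures in section 13.

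**Conclusion.** The point holds as a wording error in an entry requirement, limited to DTC and MTC patients with prior palliative radiotherapy outside the head and neck. As written, 29 days or more fails. That conclusion needs no assumption beyond the ordinary meaning of the clause.

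The narrower windows of 1, 4, 8 and 14 passing dates rest on the assumed gap, on reading *within* inclusively both times, and on exclusion 5 being applied without its discretion. The 15-day figure rests on the last two and on the specific clause displacing the general one, with dosing on the day of randomization.

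The 8-week head-and-neck rule and the anaplastic discretion are sound. No design figure, frequency, toxicity or response-rate effect is claimed.

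A reader might also take the steroid threshold in 6.6, whose comparison sign appears opposite to that in 6.7, as a second reversal of the same kind. That rests on one symbol in text extracted from a PDF, and a symbol is visibly lost nearby in 6.5. It cannot be established as an error in the plan and is not part of this point.

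**What to change.** In the DTC/MTC paragraph of 6.8.3, replace *within* by *at least* in the clause on radiotherapy to other sites, so that it sets a 4-week minimum before randomization. Leave the 8-week head-and-neck minimum and the anaplastic discretion as they are.

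The cost is one phrase at the next amendment. If both current sentences are being applied, some patients irradiated outside the head and neck would wait longer, by at most the randomization-to-dose gap and never more than 13 days under the assumptions above. Head-and-neck cases wait no longer than now. In return, patients at 29 days or more meet the rule.

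Exclusion 5 would still state a shorter minimum than 6.8.3, so a patient at 15 to 27 days would pass the first and fail the second. Two minimums can stand together with the stricter governing. A cross-reference from exclusion 5 to 6.8.3 would help but is optional.

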## 6.9 Holding Study Treatment

Following disease control (i.e., stable disease or response) sustained over the course of a year or more of therapy (or as determined by the investigator), the investigator may decide to hold study treatment for an extended period of time. In this case, imaging will be continued with timing at investigator's discretion. The investigator may choose to restart study treatment based on scan results.

## 7. ADVERSE EVENTS: LIST AND REPORTING REQUIREMENTS

Adverse event (AE) monitoring and reporting is a routine part of every clinical trial.

### 7.1 Adverse Event Characteristics

- **CTCAE term (AE description) and grade:** The descriptions and grading scales found in the revised NCI Common Terminology Criteria for Adverse Events (CTCAE) version 4.0 will be utilized for AE reporting. All appropriate treatment areas should have access to a copy of the CTCAE version 4.0. A copy of the CTCAE version 4.0 can be downloaded from the CTEP web site

---

CONFIDENTIAL

*This document is confidential. Do not disclose or use except as authorized.* IRB APPROVED

[http://ctep.cancer.gov/protocolDevelopment/electronic\\_applications/ctc.htm](http://ctep.cancer.gov/protocolDevelopment/electronic_applications/ctc.htm).

- **Attribution** of the AE:
  - Definite – The AE is clearly related to the study treatment.
  - Probable – The AE is likely related to the study treatment.
  - Possible – The AE may be related to the study treatment.
  - Unlikely – The AE is doubtfully related to the study treatment.
  - Unrelated – The AE is clearly NOT related to the study treatment.

## 7.2 Unanticipated/Life-Threatening Problems

In the event of an unanticipated problem or life-threatening complications, treating investigators must immediately notify the Overall PI.

## 7.3 Multi-Center Trial Requirements

Each participating institution must abide by the reporting requirements set by the DF/HCC. This applies to any medical event equivalent to an unexpected grade 2 or 3 with a possible, probable or definite attribution, unexpected grade 4 toxicities, and grade 5 (death) regardless of study phase or attribution.

## 7.4 DF/HCC Adverse Event Reporting Guidelines

Investigative sites within DF/HCC will report AEs directly to the DFCI Office for Human Research Studies (OHRs) per the DFCI IRB reporting policy.

Other investigative sites will report AEs to their respective IRB according to the local IRB's policies and procedures in reporting adverse events. A copy of the submitted institutional AE form should be forwarded to the Overall PI within the timeframes detailed in the table below.

Attribution	DF/HCC Reportable Adverse Events(AEs)				
	Gr. 2 & 3 AE Expected	Gr. 2 & 3 AE Unexpected	Gr. 4 AE Expected	Gr. 4 AE Unexpected	Gr. 5 AE Expected or Unexpected
Unrelated Unlikely	Not required	Not required	5 calendar days #	5 calendar days	24 hours*
Possible Probable Definite	Not required	5 calendar days	5 calendar days #	5 calendar days	24 hours*

# If listed in protocol as expected and not requiring expedited reporting, event does not need to be reported.

\* For participants enrolled and actively participating in the study **or** for AEs occurring within 30 days of the last intervention, the AE should be reported within 1 business day of learning of the event.

The Overall PI will submit AE reports from outside institutions to the DFCI OHRs according to DFCI IRB policies and procedures in reporting adverse events.

---

CONFIDENTIAL

*This document is confidential. Do not disclose or use except as authorized.*

IRB APPROVED

## **7.5 Expected Toxicities**

Expected adverse events are those that have been previously identified as resulting from administration of the agent. Consistent with the mechanism of action of nivolumab and ipilimumab, the most frequently reported drug-related adverse events observed in clinical trials are those associated with activation of the immune system. The most common types of immune-mediated adverse events include endocrinopathies, diarrhea/colitis, hepatitis, pneumonitis, nephritis and rash. In the combination regimen, the frequency and intensity of these events may vary and depend on the specific dose and schedule used.

Management of these expected toxicities are described in Appendix B.

Please refer to the Investigator's Brochures and/or Package Inserts for more information on adverse events related to the study drugs.

## **7.6 Routine Adverse Event Reporting**

Investigators will assess the occurrence of AEs and SAEs at all participant evaluation time points during the study.

All AEs and SAEs whether reported by the participant, discovered during questioning, directly observed, or detected by physical examination, laboratory test or other means, will be recorded in the participant's medical record and on the appropriate study-specific case report forms.

The descriptions and grading scales found in the CTEP Active Version of the NCI Common Terminology Criteria for Adverse Events (CTCAE version 4.0) will be utilized for AE reporting. The CTEP Active Version of the CTCAE version 4.0 is identified and located on the CTEP website at:

[http://ctep.cancer.gov/protocolDevelopment/electronic\\_applications/ctc.htm](http://ctep.cancer.gov/protocolDevelopment/electronic_applications/ctc.htm).

All appropriate treatment areas should have access to a copy of the CTEP Active Version of CTCAE.

All Adverse Events **must** be reported in routine study data submissions to the Overall PI on the toxicity case report forms. **AEs reported through expedited processes (e.g., reported to the IRB, FDA, etc.) must also be reported in routine study data submissions.**

